4.3 Dose Limiting Toxicity

DLT will be defined as any of the following adverse events that are not clearly unrelated to drug administration or treatment-emergent from lenalidomide and constitute a change from baseline irrespective of outcome. For the purpose of dose-escalation decisions and MTD determination, only DLTs that occur before 14 days after the last dose of lenalidomide administration will be taken into account.

1. Grade 3 or greater nausea, diarrhea, or vomiting despite the use of maximal medical intervention;
2. Grade 3 or greater acute GVHD despite the use of maximal medical intervention;
3. Any other clinically significant nonhematologic toxicity of grade 3 or greater considered not related to the underlying disease or intercurrent illness;
4. Grade 3 or greater neutropenia
5. Grade 4 thrombocytopenia or platelet count ≤ 50 thou/mm³ by day 28 of lenalidomide administration; or
6. Any treatment-related effect leading to a subject missing 3 or more doses of lenalidomide.

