5.2 Inclusion Criteria

- 1) Subjects must be at least 18 years of age;
- 2) Subjects must be 60 (+/- 7) days post-allogeneic transplant from any donor source;
- 3) Subjects must have either:
 - a) High risk CD34+ AML (*de novo* or secondary, and any WHO 2008 classification excluding acute promyelocytic leukemia, see Appendix A: AML WHO 2008 Classification System³). High risk AML is defined as (a) disease status beyond complete remission (CR) #1 at transplant or (b) treatment related AML or (c) presence of adverse cytogenetics including *inv(3)*; *t(3;3)*; *t(6;9)*; *t(v;11)*; -5 or *del(5q)*; -7; *abnl(17p)* or complex karyotype; or
 - b) High risk CD34+ MDS (WHO 2008 classification, see Appendix B: MDS WHO 2008 Classification System³⁴). High risk is defined as (a) blast count $\geq 5\%$ at the time of transplant or (b) treatment related MD or (c) presence of adverse cytogenetics including *-7/del7q* or complex karyotype;
- 4) For AML subjects, they must have a documented CR within 45 days prior to allo-HCT;
- 5) For MDS subjects, they must have $< 20\%$ myeloblasts in the bone marrow within 45 days prior to allo-HCT;
- 6) Subject Karnofsky performance status must be ≥ 70 (see Appendix E: Karnofsky Performance Status);
- 7) Subjects must be platelet transfusion independent (Platelet transfusion independence is defined as 7 days or greater without a platelet transfusion);
- 8) Neutrophil count ≥ 1.0 thou/mm³ and platelet count ≥ 30 thou/mm³;
- 9) Subjects must have total bilirubin ≤ 2 mg/dL;

- 10) Subjects must have serum AST and ALT levels ≤ 2.5 times upper limit of normal;
- 11) Subjects must have serum creatinine < 2.5 times upper limit of normal and a calculated creatinine clearance ≥ 30 ml/min by Cockcroft-Gault formula (see [Appendix I: Cockcroft-Gault Creatinine Clearance Calculation](#));
- 12) All study participants who will receive lenalidomide based on the CD34+ chimerism testing must be registered into the mandatory Revlimid REMS[®] program, and be willing and able to comply with the requirements of the REMS[®] program;
- 13) Females of child-bearing potential (*i.e.*, women who are pre-menopausal or not surgically sterile) may participate, provided they meet the following conditions:
 - a) Females of reproductive potential must adhere to the scheduled pregnancy testing as required in the Revlimid REMS[®] program; and
- 14) Written, voluntary informed consent, willingness, and ability to comply with all study procedures.

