6.2 Instructions for initiation of lenalidomide

Lenalidomide may begin if each of the following criteria are met:

- The ANC is ≥ 1.0 thou/mm³;
- The platelet count is ≥ 50 thou/mm³;
- The CD34+ donor chimerism is $\leq 90\%$ at day +60 or +120 (± 7 days) post-transplant.

Lenalidomide dosing will continue as scheduled unless a DLT occurs.

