9.2.2.2 Clinical Laboratory Measurements

All clinical laboratory assessments are outlined in the Schedule of Events.

Hematology assessments will be performed at Screening and then weekly during lenalidomide administration and for 3 weeks after therapy is completed. The hematology assessments will include:

- Complete blood count including hemoglobin, hematocrit, WBC absolute differential and platelet count.

Blood chemistry assessments will be performed at screening and then weekly during lenalidomide administration. The chemistry assessments will include:

- Electrolytes: (sodium, potassium, calcium, magnesium, phosphorous, bicarbonate, and chloride);
- Renal function: (BUN, creatinine, and uric acid);
- Liver function: SGOT (also known as AST), SGPT (also known as ALT), total bilirubin; and
- Alkaline phosphatase.

Serum pregnancy test for females of childbearing potential will be performed at Screening and must follow the pregnancy testing requirements as outlined in the Revlimid REMS® program material.

Abnormal values and/or noteworthy changes will be graded according to the Common Terminology Criteria for Adverse Events v4.0 (CTCAE).

Abnormalities of laboratory values:

The Investigator shall classify laboratory values occurring outside of the normal range obtained for the safety assessment as:

- “Abnormal, but not clinically significant” or
- “Abnormal and clinically significant”

Laboratory abnormalities should be judged as “clinically significant” if they lead to treatment modifications, therapeutic actions, or if additional diagnostic measures are required for their resolution and in the Investigator’s opinion is relevant for the clinical study.

Each clinically relevant laboratory abnormality must be recorded as a separate AE if it fits within the AE criteria outlined in Section 10.1 of the protocol and is not already described by another documented AE.

Hematology and serum chemistry assessments will be performed according to the standard operating procedures by the validated local laboratory.

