13.3 Analysis Methods

13.3.1 Safety

Safety evaluation will include monitoring for adverse events, scheduled laboratory assessments, vital sign measurements, and physical examinations. The intensity of adverse changes in physical signs or symptoms will be graded according to the CTCAE version 4. For all other adverse events not listed in the CTCAE, the intensity of these events will be assessed by the Investigator using a 5-point scale as described in Section 10.3.2.

The number of adverse events and the incidence of adverse events will be summarized. Adverse events will be summarized by maximum intensity (as described in Section 10.3.2) and relationship to study drug for each treatment group. Separate summaries will be provided for all adverse events, serious adverse events, treatment-related adverse events, and other significant adverse events (*e.g.*, adverse events leading to study discontinuation).

Clinical laboratory results will be listed by subject or, as appropriate, summarized descriptively by treatment group, which will include a display of change from baseline. Laboratory values outside of the normal ranges will be identified. Clinically significant hematologic laboratory abnormalities (*i.e.*, meet Grade 3, 4, or 5 criteria according to CTCAE v.4) will be listed and summarized.

Physical examination, vital sign, and GVHD data will be listed for each subject at each study visit. If appropriate, descriptive statistics for vital signs, both observed values and changes from baseline, will be summarized by treatment group.

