16.8 Appendix H: RBC Transfusion Independence

RBC transfusion independence and RBC transfusion dependence are defined according to modified IWG criteria,³⁶ as described below:

Definitions of RBC transfusion status at screening:

- **RBC transfusion independence:**
 - Subjects with hemoglobin > 90 g/L (9.0 g/dL);
 - Subjects who received ≤ 1 RBC transfusion during the previous 8 weeks (56 days).
- **RBC transfusion dependence:**
 - Subjects with hemoglobin ≤ 90 g/L (9.0 g/dL);
 - Subjects who received ≥ 2 RBC transfusions during the previous 8 weeks (56 days).

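### The Grade 3-5 haematology summary has no post-dose window and no comparison with the pre-dose grade, so cytopenia already present after transplant would be counted in it

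*Combined protocol and SAP*

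**What the plan says.** Section 13.3.1 handles laboratory data in two steps. Laboratory results in general are listed by subject or, where appropriate, "summarized descriptively by treatment group, which will include a display of change from baseline". Haematology then gets its own rule: clinically significant abnormalities are those that "meet Grade 3, 4, or 5 criteria according to CTCAE v.4) will be listed and summarized". The definition is introduced by an i.e., so the grade is the whole criterion.

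The counts come from section 9.2.2.2, which names a "Complete blood count including hemoglobin, hematocrit, WBC absolute differential and platelet count". On timing, "Hematology assessments will be performed at Screening and then weekly during lenalidomide administration and for 3 weeks after therapy is completed". The Schedule of Events also places a CBC with differential at C1D1.

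Two other definitions in the protocol do look at what was there before. Section 10.1.1 limits an adverse event to something that is new or has become worse during observation. Section 4.3 requires that a DLT "constitute a change from baseline irrespective of outcome".

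The haematology limits at entry (section 5.2) are "Neutrophil count ≥ 1.0 thou/mm³ and platelet count ≥ 30 thou/mm³". To start drug (section 6.2), "The ANC is ≥ 1.0 thou/mm³" and platelets must be at least 50 thou/mm³. Neither section sets a limit for haemoglobin, total white cells or lymphocytes.

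**The concern.** Subjects are enrolled at Day 60 ± 7 after an allogeneic transplant, when low counts may have causes unrelated to lenalidomide. Followed literally, section 13.3.1 gives the same weight to a subject whose haemoglobin was Grade 3 before and after the first dose as to one who fell to Grade 3 on drug. Its wording does not exclude even a screening value.

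Safety is part of the primary objective, and sections 2.1.2 and 6.3 name haematological toxicity as a known effect of the drug. A graded summary that mixes pre-existing and new cytopenia is hard to read for that purpose. In groups this small, the chance of who entered which cohort could produce or mask an apparent dose pattern. The summary could also disagree with the adverse event tables about the same subject, because those tables do require onset or worsening.

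**Working it through.** The plan states no figure on this point, so there is none to reproduce. The check is a comparison of the rules, followed by an illustration of size.

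**Rules side by side**

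| Output | Condition relative to the pre-dose state |
|---|---|
| Adverse events (10.1.1) | must be new or worse |
| DLTs (4.3) | must be a change from baseline |
| General laboratory summary (13.3.1) | change from baseline displayed |
| Grade 3-5 haematology (13.3.1) | none; no time window |

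**Which counts are open**

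- Neutrophils: limit of 1.0 thou/mm³ at entry and at start.
- Platelets: limit of 30 thou/mm³ at entry and 50 thou/mm³ at start.
- Haemoglobin, total white cells, lymphocytes: measured, with no limit at either point. Any grade is therefore admissible before dosing. The CTCAE cut-offs are not in the documents and are not needed for this step.

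**Weight of one subject.** Section 13.1 plans 3 to 6 subjects per level. If a per-level rate is produced, one subject already at the grade adds 1/6 = 17 percentage points or 1/3 = 33 percentage points.

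**How often a level would contain such a subject.** Let b be the share of subjects at Grade 3 or worse before the first dose in a count that has no limit. The documents do not give b, so the values below are assumptions. The chance of at least one among n subjects is 1 − (1 − b)^n. The expected number among the maximum of 24 is 24b.

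| Assumed b | n = 3 | n = 6 | Expected among 24 |
|---|---|---|---|
| 5% | 14% | 26% | 1.2 |
| 10% | 27% | 47% | 2.4 |
| 20% | 49% | 74% | 4.8 |
| 30% | 66% | 88% | 7.2 |

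**Effect on an expected rate.** Let w be the chance that a subject below Grade 3 before dosing reaches Grade 3 or worse on drug, and assume that subjects already there do not worsen further.

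- As written: b + (1 − b)w.
- Counting worsening only: (1 − b)w.
- The difference is b. With w = 0 and b = 20%, the rates are 20% and 0%. With w = 10% and b = 20%, they are 0.20 + 0.80 × 0.10 = 28% and 0.80 × 0.10 = 8%.

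Here b is the share for whatever is tabulated. If haemoglobin, white cells and lymphocytes are shown separately, each has its own b, no larger than the pooled one.

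**The case against.** The strongest reply is that this is one sentence in a section that presents itself as an overview, and that most of the protection exists elsewhere. Several parts of that stand.

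- **Adverse event tables.** These are summarised by maximum intensity, relationship and treatment group, and only new or worsened events qualify. Treatment-emergent cytopenia judged clinically significant would appear there.
- **Baseline is visible.** The change-from-baseline display and the by-subject listing let a reader of at most 24 subjects trace pre-dose values by hand. Neither alters the graded count.
- **No rate is specified.** The Grade 3-5 sentence gives no denominator and does not itself say that the summary is by treatment group; that comes from the sentence on laboratory results in the same paragraph. The 17 to 33 points arise only if a per-level rate is reported.
- **Recording every Grade 3 or worse value** is a defensible cautious choice for a phase I listing, and the fix should keep it.

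A reader might go further in three ways that the documents do not support. One is to infer that dose finding is distorted: it is not, since DLTs require a change from baseline. Another is to extend the point equally to neutropenia and thrombocytopenia: those two counts have limits before dosing. The third is to read Appendix H, with its "Definitions of RBC transfusion status at screening", as proof that severely anaemic subjects are expected. No eligibility criterion, endpoint or analysis refers to that appendix. It sets categories at a haemoglobin of 9.0 g/dL, which shows neither how common low haemoglobin will be nor that anyone starts at Grade 3.

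**Conclusion.** The point holds for the descriptive Grade 3-5 haematology summary and for nothing beyond it. As worded, the summary counts pre-existing low haemoglobin, total white cells or lymphocytes together with new toxicity, which departs from the protocol's own approach to adverse events and DLTs. The weight of each such subject is fixed by the cohort size. How many there will be is unknown, and the prevalence range above is illustrative only. To say that the reported rates will be inflated by a particular amount would need both a baseline prevalence and a commitment to per-level rates, and the documents give neither. The correction is worth making because safety is a primary aim and the data needed are already scheduled.

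**What to change.** In section 13.3.1:

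1. Define baseline for haematology as the last value before the first dose of lenalidomide, using the C1D1 CBC where it is drawn before dosing.
2. Keep the by-subject listing of all Grade 3-5 values and flag those obtained before the first dose.
3. In the summary, by dose level, count Grade 3-5 values obtained after the first dose whose grade is higher than the baseline grade.
4. Add a shift table by dose level of baseline grade against worst post-dose grade.

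The cost is a few lines of wording and one table from blood counts already collected. No visit, test or treatment rule changes. The downside is small but should be stated: a subject already at Grade 3 or higher who stays at that grade, or who recovers and falls back to it on drug, is not counted as new. The shift table shows those two courses identically, so they can be told apart only in the retained listing.

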13.3.2 Efficacy

All efficacy endpoints will be summarized descriptively using frequency distributions. In addition, 95% confidence intervals will be provided for the proportion of each response/improvement.

14. EMERGENCY PROCEDURES

14.1 Emergency Contact

In emergency situations, the treating physician should contact the Principal Investigator by telephone at the number listed on the title page of the protocol.

14.2 Emergency Identification of Investigational Products

This is an open-label study; therefore, study drug will be identified on the package labeling.

14.3 Emergency Treatment

During and following a subject's participation in the study, the treating physician and/or institution should ensure that adequate medical care is provided to a subject for any adverse events, including clinically significant laboratory values, related to the study.

15. ADMINISTRATIVE CONSIDERATIONS

15.1 Good Clinical Practice

The procedures set out in this study protocol pertaining to the conduct, evaluation, and documentation of this study are designed to ensure that the Principal Investigator and Co-Investigators abide by Good Clinical Practice (GCP), as described in International Conference on Harmonization (ICH) Guideline E6, the US Code of Federal Regulations (CFR), and in accordance with the general ethical principles outlined in the Declaration of Helsinki. The study will receive approval from an Institutional Review Board (IRB) prior to commencement. The Principal Investigator will conduct all aspects of this study in accordance with applicable national, state, and local laws of the pertinent regulatory authorities.

15.2 Delegation of Investigator Responsibilities

The Principal Investigator will ensure that all persons assisting with the study are adequately informed about the protocol, any amendments to the protocol, the study treatments, and their study-related duties and functions. The Principal Investigator will maintain a list of Sub-Investigators and other appropriately qualified persons to whom he has delegated significant study-related duties.

15.3 Subject Information and Informed Consent

The Principal Investigator or designee must obtain valid informed consent of a subject prior to any study related procedures occur as per GCP set forth in the CFR and ICH guidelines.

Documentation that informed consent occurred prior to the subject's entry into the study and the informed consent process will be recorded in the subject's source documents. The original informed consent form will be signed and dated by the subject and by the person conducting the consent discussion prior to entry into the study. An informed consent document that includes information about the study and investigational drug will be prepared and given to each potential subject. This document will contain all ICH, GCP, and locally required regulatory elements. The document must be in a language understandable to the subject and must specify who informed the subject. The original informed consent form must be maintained in the Investigator's study files. A copy of the informed consent document must be given to the subject.

15.4 Confidentiality

Each subject will be assigned a unique acrostic that will contain no protected health information. The Principal Investigator will retain a copy of the acrostic key in a locked office. Study files stored on a computer will be stored in accordance with local data

protection laws. Subjects will be told that the IRB, Data Integrity and Safety Committee, or regulatory authorities may inspect their medical records to verify the information collected, and that all personal information made available for inspection will be handled in strictest confidence and in accordance with local data protection law.

15.5 Protocol Amendments

Once the study has started, amendments should be made only in exceptional cases. The changes then become part of the study protocol.

15.6 Record Retention

Essential documents will be retained by the Principal Investigator for a minimum of 5 years have elapsed since study closure. Essential documents include the following:

- Signed informed consent documents for all subjects;
- Subject identification code list, screening log, and enrollment log;
- Record of all communications between the Principal Investigator and the IRB;
- Composition of the IRB;
- Record of all communications between the Principal Investigator and the DISC;
- Composition of the DISC;
- List of Sub-Investigators and other appropriately qualified persons to whom the Principal Investigator has delegated significant study-related duties, together with their roles in the study, curriculum vitae, start/stop date(s) of participation, and their signatures;
- Copies of CRFs and of documentation of corrections for all subjects (for electronic case report forms [eCRF], electronic files of the eCRF and audit trails will be utilized and provided to the site, as necessary);
- Drug accountability records;
- Record of any blood samples retained; and
- Other source documents (subject records, hospital records, laboratory records, etc.).

16. APPENDICES

16.1 Appendix A: AML WHO 2008 Classification System³

- Acute myeloid leukemia with recurrent genetic abnormalities
 - AML with t(8;21)(q22;q22); *RUNX1-RUNX1T1*
 - AML with inv(16)(p13.1q22) or t(16;16)(p13.1;q22); *CBFB-MYH11*
 - APL with t(15;17)(q22;q12); *PML-RARA*
 - AML with t(9;11)(p22;q23); *MLLT3-MLL*
 - AML with t(6;9)(p23;q34); *DEK-NUP214*
 - AML with inv(3)(q21q26.2) or t(3;3)(q21;q26.2); *RPN1-EVI1*
 - AML (megakaryoblastic) with t(1;22)(p13;q13); *RBM15-MKL1*
- Acute myeloid leukemia with myelodysplasia-related changes
- Therapy-related myeloid neoplasms
- Acute myeloid leukemia, not otherwise specified
 - AML with minimal differentiation
 - AML without maturation
 - AML with maturation
 - Acute myelomonocytic leukemia
 - Acute monoblastic/monocytic leukemia
 - Acute erythroid leukemia
 - Pure erythroid leukemia
 - Erythroleukemia, erythroid/myeloid
 - Acute megakaryoblastic leukemia
 - Acute basophilic leukemia
 - Acute panmyelosis with myelofibrosis
- Myeloid sarcoma
- Myeloid leukemia associated with Down syndrome

16.2 Appendix B: MDS WHO 2008 Classification System³⁴

Disease	Blood	Bone Marrow
Refractory Cytopenia with Unilineage Dysplasia (RCUD): 
 • Refractory Anemia (RA) • Refractory Neutropenia (RN) • Refractory Thrombocytopenia (RT) 	Unicytopenia or Bicytopenia No or rare blasts (< 1%)	Unilineage dysplasia \geq 10% < 5% blasts < 15% of erythroid are RS
Refractory Anemia with Ringed Sideroblasts (RARS)	Anemia No blasts	\geq 15% of erythroid are RS Erythroid dysplasia only < 5% blasts
Refractory Cytopenia with Multilineage Dysplasia (RCMD)	Cytopenia(s) No or rare blasts (< 1%) No Auer rods Absolute monocyte count < 1000	Dysplasia in \geq 10% of cells in \geq 2 lineages < 5% blasts No Auer rods \pm 15% of erythroid are RS
Refractory Anemia with Excess Blasts 1 (RAEB-1)	Cytopenia(s) < 5% blasts No Auer rods Absolute monocytes count < 1000	Unilineage or multilineage dysplasia 5% - 9% blasts No Auer rods
Refractory Anemia with Excess Blasts 2 (RAEB-2)	Cytopenia(s) 5% - 9% blasts Auer rods \pm Absolute monocytes count < 1000	Unilineage or multilineage dysplasia 10% - 19% blasts Auer rods \pm
Myelodysplastic Syndromes Unclassifiable (MDS-U)	Cytopenias < 1% blasts	Dysplasia < 10% Cytogenetic abnl c/w MDS < 5% blasts
MDS associated with del(5q)	Anemia Platelets: normal or increased No or rare blasts (< 1%)	Megas: normal to increased < 5% blasts Isolated del(5q) No Auer rods

16.3 Appendix C: AML Response Criteria According to IWG³⁵**Hematologic Response According to IWG Criteria for AML**

Response Criterion	Time of Assessment	Neutrophils (μL)	Platelets (μL)	Bone Marrow Blasts (%)	Other
Early treatment assessment	7-10 days after therapy	NA	NA	<5	
Morphologic leukemia-free state	Varies by protocol	NA	NA	<5	Flow cytometry EMD
Morphologic CR	Varies by protocol	>1,000	>100,000	<5	Transfusion EMD
Cytogenetic CR	Varies by protocol	>1,000	>100,000	<5	Cytogenics—normal, EMD
Molecular CR	Varies by protocol	>1,000	>100,000	<5	Molecular—negative, EMD
Partial remission	Varies by protocol	>1,000	>100,000	>50 or decrease to 5-25	Blasts <5% if Auer rod positive

Key: AML=acute myelogenous leukemia; CR=complete remission; EMD=extramedullary disease; IWG=International Working Group; NA=not applicable

